2.2 Analysis sets

2.2.1 Full analysis set

The Full Analysis Set (FAS) comprises all patients who received at least one dose of the assigned combination of study drugs (ribociclib + everolimus + exemestane) i.e. a patient should have taken atleast one dose of each of the components from the study treatment.

2.2.2 Safety set

The Safety Set includes all patients who received at least one dose of any of the components from the investigational treatment, and have at least one valid post-baseline safety assessment.

The statement that a patient had no AEs (on the AE eCRF) constitutes a safety assessment.

2.2.3 DLT-determining analysis set

The DLT-determining set (DDS) includes all patients from the safety set in the dose escalation part who either completed a minimum exposure requirement and have sufficient safety evaluations in the first cycle or discontinued prematurely due to a dose limiting toxicity (DLT).

A patient is considered to have met the minimum exposure requirement if having received at least 75% of the planned combination doses (i.e. 21 out of 28 planned daily doses) for all compounds administered together (same day): ribociclib, everolimus and exemestane. The length of a cycle is 28 days.

Patients who do not experience a DLT during the first cycle will be considered to have sufficient safety evaluations if they have been observed for ≥ 28 days following the first dose, and are considered by both the Sponsor and Investigators to have enough safety data to conclude that a DLT did not occur.

Note: This analysis set will only use to display dose limiting toxicities for phase I.

[figure not shown]

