6.2.1 Criteria for dose escalation and determination of MTD(s)/RP2D

6.2.1.1 MTD definition

The MTD is defined as the highest combination drug dosage not causing medically unacceptable DLTs in more than 33% of the treated patients in the first cycle of treatment. AEs and laboratory abnormalities considered to be DLTs are defined in [Table 6-4](#). Only one RP2D will be tested in the Phase II.

In the dose escalation a total of 6 patients will be treated at dose-level 1 (cohort A). Patients must complete a minimum of one cycle of treatment with the minimum safety evaluation and drug exposure or have had a DLT within the first cycle of treatment to be considered evaluable for dose escalation decisions.

- If $\leq 33\%$ of patients experience a DLT in cohort A (dose level 1), the dose will be escalated to the next level cohort B (dose level +1) where 3 patients will be enrolled.
- If $\leq 33\%$ patients experience DLTs in cohort B, an additional 3 patients will be treated at the same dose level.
- If $\leq 33\%$ patients experience a DLT in both cohorts, then the optimal treatment dose based on tolerability and safety profile after two cycles will move into Phase II.
- If $>33\%$ patients experience DLTs in both cohorts, the dose will be de-escalated to the next level down .

Dose escalation and R2PD decisions will be/were made jointly by the independent Data Monitoring Committee, Steering Committee, and Novartis study personnel.

In the dose de-escalation (cohort C), the starting dose of ribociclib and everolimus are based upon a review of the safety, tolerability, and PK observed in the clinical studies outlined in [Section 1.2](#). Because of the potential drug interaction between ribociclib and everolimus that may inhibit the metabolism of everolimus and increase drug exposure by approximately 2-fold, if ribociclib is dosed at 200mg (based on CLEE011X2106) from the standard dose recommended in the treatment of breast cancer of 10 mg QD ([Section 1.2.2](#)). The starting dose of ribociclib is supported by a recommendation from the CLEE011X2106 study ([Section 1.2.4](#))

The MTD is defined as the highest combination drug dosage not causing medically unacceptable DLTs in more than 33% of the treated patients in the first cycle of treatment. AEs and laboratory abnormalities considered to be DLTs are defined in [Table 6-4](#). Only one RP2D will be tested in the Phase II.

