6.2.2 Definitions of dose limiting toxicities (DLTs)

A dose-limiting toxicity (DLT) is defined as an adverse event or abnormal laboratory value assessed as having a reasonably possible relationship to the study medication(s) and is unrelated to disease, disease progression, inter-current illness, or concomitant medications that occurs within the first 28 days of treatment (cycle 1) with ribociclib + everolimus + exemestane and meets any of the criteria included in [Table 6-4](#). National Cancer Institute Common Terminology Criteria for Adverse events (NCI CTCAE) version 4.03 will be used for all grading.

Whenever a patient experiences toxicity that fulfills the criteria for a DLT, treatment with the study drug combination will be interrupted and the toxicity will be followed up as described in [Section 6.2.3](#). For the purposes of dose escalation and determination of the MTD(s), DLTs that occur during cycle 1 will be necessarily considered, including those in which the event started in Cycle 1 and the confirmation of the DLT occurs in a subsequent cycle. The investigator must notify the Sponsor immediately of any unexpected CTCAE grade ≥ 3 adverse events or laboratory abnormalities. Prior to enrolling patients into a higher dose level, CTCAE grade ≥ 2 adverse events will be reviewed for all patients at the current dose level.

Patients must have completed $\geq 75\%$ of ribociclib + everolimus + exemestane in cycle 1 (≥ 21 days out of 28 days) to be considered for DLT evaluation. Patients not evaluable for DLT could be replaced after discussing with the steering committee.

Appropriate eligibility criteria and specific DLT definitions, as well as specific dose modification and stopping rules are included in this protocol. Recommended guidelines for prophylactic or supportive treatment for expected toxicities, including management of study drug induced adverse events are provided in [Table 6-5](#) and [Table 6-6](#).

For patients who do not tolerate the protocol-specified dosing schedule, dose adjustments are permitted in order to allow the patient to continue the study treatment. These changes must be recorded on the Dosage Administration Record eCRF.

Table 6-4 Criteria for defining Dose Limiting Toxicities

TOXICITY	DLT CRITERIA
	CTCAE grade 3 thrombocytopenia with bleeding

Hematology	Febrile neutropenia (decrease in neutrophils associated with fever $\geq 38.5^{\circ}\text{C}$, ANC $<1.0 \times 10^9/\text{L}$)

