10.1.3 DLT-determining analysis set

The DLT-determining set (DDS) includes all patients from the safety set in the dose escalation part who either completed a minimum exposure requirement and have sufficient safety evaluations in the first cycle or discontinued prematurely due to a dose limiting toxicity (DLT).

A patient is considered to have met the minimum exposure requirement if having received at least 75% of the planned combination doses (i.e. 21 out of 28 planned daily doses) for all compounds administered together (same day): ribociclib, everolimus and exemestane. The length of a cycle is 28 days.

Patients who do not experience a DLT during the first cycle will be considered to have sufficient safety evaluations if they have been observed for ≥ 28 days following the first dose, and are considered by both the Sponsor and Investigators to have enough safety data to conclude that a DLT did not occur.

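### The DLT-determining set leaves out a patient whose Cycle 1 DLT led to a long hold without permanent discontinuation, so the reported Phase I DLT rate can be too low

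*SAP*

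**What the plan says.** The SAP (2.2.3) and the protocol (10.1.3) define the DDS in the same way. A Phase I safety-set patient enters by one of two routes:

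- minimum exposure in Cycle 1, set at "at least 75% of the planned combination doses (i.e. 21 out of 28 planned daily doses") with all three drugs taken on the same day, plus sufficient safety evaluations; or
- having "discontinued prematurely due to a dose limiting toxicity (DLT").

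Sufficient safety evaluation is spelled out only for patients without a DLT: "Patients who do not experience a DLT during the first cycle will be considered to have sufficient safety evaluations if they have been observed for" at least 28 days.

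Four other passages bear on the point.

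- Protocol 6.2.2 states the action on a DLT: "treatment with the study drug combination will be interrupted and the toxicity will be followed up".
- The same section requires at least 75% "of ribociclib + everolimus + exemestane in cycle 1" before a patient counts for DLT evaluation. It makes no exception for a patient who had a DLT, and it allows non-evaluable patients to be replaced.
- Protocol 6.2.1.1 uses a different rule. A patient must complete a cycle with the minimum evaluation and exposure, "or have had a DLT within the first cycle of treatment to be considered evaluable for dose escalation decisions". It repeats this for cohort C.
- SAP 3.5.2.1 states that same evaluability rule, and then says that the DLT listing and tables are based on the DDS.

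**The concern.** An analysis set for DLT incidence should not lose a patient because of what followed from the DLT. Here the event triggers a hold, the hold lowers exposure, and low exposure can remove the patient from both numerator and denominator. Patients without a DLT have no matching mechanism that takes out events, so the error runs in one direction only. The table affected is the one that reports the Phase I primary endpoint, in cohorts of 3 to 6 planned patients, where one lost event moves the rate by many percentage points and can carry it across the 33% limit that defines the MTD.

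**Working it through.** **1. The exposure threshold.** 0.75 × 28 = 21, which reproduces the plan's figure. A patient fails it when 28 − missed < 21, that is, with 8 or more missed same-day doses. For one unbroken hold of L days starting on day s, missed doses in Cycle 1 = min(L, 29 − s). This reaches 8 only if L ≥ 8 and s ≤ 21. A hold of 7 days or less, or one starting on day 22 or later after full dosing, leaves the patient in the set. Holding ribociclib and everolimus alone counts as missed, because the rule asks for all three drugs on the same day.

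**2. Whether a hold can count as discontinuation.** It cannot. The protocol glossary defines study treatment discontinuation as permanent, and 6.2.3 distinguishes treatment that is interrupted from treatment that is permanently discontinued.

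**3. Whether the case can arise under the plan.** It can. Grade 4 neutropenia is a DLT in Table 6-4 only if it lasts more than 7 consecutive days, so at least 8. Table 6-8 holds ribociclib and everolimus for it until the count recovers, and then restarts. If that hold begins at onset, on or before day 21, at least 8 same-day doses are missed. Table 6-8 also provides for hold and restart in grade 3 febrile neutropenia, a DLT in Table 6-4. Protocol 1.2.5.1.2 reports one grade 3/4 febrile neutropenia in each of cohorts A and B. It does not say whether these were Cycle 1 DLTs or how long treatment was held.

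**4. The same patient under each rule.** Take a Cycle 1 DLT, a hold that leaves fewer than 21 same-day doses, and no permanent discontinuation.

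| Passage | Is the patient counted? |
|---|---|
| Protocol 6.2.1.1 | Yes, had a Cycle 1 DLT |
| SAP 3.5.2.1, evaluability rule | Yes, same rule |
| Protocol 6.2.2, 75% sentence | No, exposure too low and no DLT exception |
| SAP 2.2.3 and protocol 10.1.3 (DDS) | No, meets neither route |
| SAP 3.5.2.1, DLT table | No, because it uses the DDS |

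**5. Size.** With n patients, d with a DLT, and k of those d lost, the rate d/n is shown as (d − k)/(n − k), which is lower whenever k ≥ 1 and d < n. The counts below are illustrative. Six is the top of the planned cohort range, and eight is the evaluable number in each of cohorts A and B in protocol 1.2.5.1.2.

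| n | d | k | All Cycle 1 DLTs | Shown on the DDS |
|---|---|---|---|---|
| 6 | 2 | 1 | 2/6 = 33.3% | 1/5 = 20.0% |
| 6 | 3 | 2 | 3/6 = 50.0% | 1/4 = 25.0% |
| 8 | 2 | 1 | 2/8 = 25.0% | 1/7 = 14.3% |
| 8 | 3 | 1 | 3/8 = 37.5% | 2/7 = 28.6% |

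The second and fourth rows move a rate from above 33% to below it.

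For a true rate p and a share q of DLT patients lost, the apparent rate is p(1 − q)/(1 − pq). The documents give no q, so it is an assumption, shown as a range:

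| p | q = 0.25 | q = 0.50 | q = 0.75 |
|---|---|---|---|
| 33.3% | 27.3% | 20.0% | 11.1% |
| 50.0% | 42.9% | 33.3% | 20.0% |

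**The case against.** The strongest reply has four parts.

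First, the gap is narrow. A reader might infer that every DLT managed by interruption is dropped. That is not so: with 21 or more same-day doses, a DLT patient satisfies the exposure rule. Some DLT-type events also lead to discontinuation, such as grade 4 febrile neutropenia in Table 6-8, or raised transaminases with concurrent bilirubin in Table 6-11, and those patients enter by the second route. This stands, and it limits the point to long holds without discontinuation.

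Second, nothing shows that a DLT was actually missed. The documents report neither hold lengths nor the number of DLT patients below 21 doses. This also stands. The claim is that the written rule can undercount, not that it did.

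Third, a reader might infer that the recommended Phase II doses rest on a biased rate. The documents do not support that. SAP 2.2.3 limits the set to displaying Phase I DLTs. The dose-decision rule already includes any patient with a Cycle 1 DLT, and protocol 6.2.2 says that Cycle 1 DLTs must be considered for escalation and the MTD. What remains is that the 75% sentence in 6.2.2, together with its replacement provision, contradicts that rule, so the text alone does not settle which one was applied.

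Fourth, the event is not lost from all reporting. Adverse events are listed, and those leading to dose adjustment or interruption are summarised on the safety set by Phase I cohort (SAP 3.8 and 3.8.1). True, but those tables do not give the DLT rate.

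**Conclusion.** Wrong as written. The DDS definition and the 75% sentence in protocol 6.2.2 omit a route that protocol 6.2.1.1 and SAP 3.5.2.1 both state, namely a DLT within the first cycle. The patients exposed to the gap are those with a Cycle 1 DLT, 8 or more missed same-day doses in that cycle, and no permanent discontinuation because of the DLT. If there are any, the primary DLT table shows too low a rate. Losing one patient costs about 9 to 13 percentage points in the illustrative counts above (37.5 − 28.6 = 8.9; 33.3 − 20.0 = 13.3).

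This rests on two assumptions: that discontinuation means what the glossary says, and that a DLT patient with at least 21 doses is accepted as sufficiently evaluated, since the documents define that term only for patients without a DLT. The direction of the bias is certain. Its actual size is unknown and may be zero. An effect on the recommended Phase II doses is not shown.

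**What to change.** Redefine the DDS in SAP 2.2.3 as Phase I safety-set patients who either

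- had a DLT in Cycle 1, regardless of exposure or later treatment, or
- met the minimum exposure and had sufficient safety evaluations.

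Make the same change in protocol 10.1.3, and limit the 75% sentence in protocol 6.2.2 to patients without a Cycle 1 DLT, so that both agree with protocol 6.2.1.1 and SAP 3.5.2.1. Events that start in Cycle 1 and are confirmed later should count, as 6.2.2 already provides.

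The cost is one sentence in each of three places. No new data and no change to patient management are needed. The reported DLT rate may be higher than under the present definition, and it cannot be lower.

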2.2.4 Pharmacokinetic analysis set

The PK analysis set (PAS) consists of all patients who have at least one blood sample providing evaluable PK data. The PAS will be used for summaries of PK data (tables and figures) as well as for listings of derived parameters.

2.2.5 Per-protocol set

A subset of Full Analysis Set (FAS) excluding major protocol violations.

Supportive analyses of the primary endpoint (i.e., CBR) may be performed using Per- protocol set (PPS).

2.2.7 Subgroup of interest

Not Applicable.

2.3 Concomitant medications with specific impact on the analysis

2.3.1 Inducers, inhibitors and substrates of CYP3A

According to the study protocol, treatment with substances which are strong inhibitors, or inducers of CYP3A4/5, or substrates of CYP3A4/5 with a narrow therapeutic window, or medications with a known risk of QT prolongation should be avoided. These substances are listed in the [Table 2-1](#). A corresponding list for programming purposes will be saved in a separate document.

However, some patients may take these substances during the treatment period so these concomitant medications will be selected via programming and tabulated and listed in the Clinical Study Report. If there is an update for the list of prohibited medications (e.g., in protocol amendment), the most up-to-date list shall be used for the Clinical Study Report.

Treatment with the prohibited substances mentioned above will be identified in the database as protocol deviations.

Table 2-1 List of prohibited medications during study drug treatment

| Category | Drug Name |
|--|---|
| Strong CYP3A4/5 inhibitors | Boceprevir, clarithromycin, cobicistat, conivaptan, danoprevir/ritonavir, darunavir/ritonavir, elvitegravir/ritonavir, grapefruit juice, idelalisib, indinavir, indinavir/ritonavir, itraconazole, ketoconazole, lopinavir/ritonavir, mibefradil, nefazodone, nelfinavir, posaconazole, ritonavir, saquinavir, saquinavir/ritonavir, telaprevir, telithromycin, tipranavir/ritonavir, troleandomycin, VIEKIRA PAK2, voriconazole |
| Strong CYP3A4/5 inducers | Avasimibe ^{2,3} , carbamazepine, mitotane, phenobarbital, phenytoin, rifabutin, rifampin (rifampicin) ³ , St. John's wort (hypericum perforatum) ³ |
| CYP3A4/5 substrates with NTI ¹ | Alfentanil, apixaban (doses >2.5 mg only), aprepitant, astemizole, cisapride, cyclosporine, diergotamine (dihydroergotamine), ergotamine, fentanyl, lomitapide, lovastatin, nicardipine, nisoldipine, pimozide, quinidine, rivaroxaban, simvastatin, sirolimus, tacrolimus, terfenadine, thioridazine |
| Medications with a known risk for QT prolongation ⁴ | Amiodarone, anagrelide, arsenic trioxide, astemizole, azithromycin, bepridil, chloroquine, cocaine, chlorpromazine, cilostazol, ciprofloxacin, cisapride, citalopram, clarithromycin, disopyramide, dofetilide, domperidone, donepezil, dronedarone, droperidol, erythromycin, escitalopram, flecainide, fluconazole, gatifloxacin, grepafloxacin, halofantrine, haloperidol, ibutilide, levofloxacin, levomethadyl, mesoridazine, methadone, moxifloxacin, ondansetron (i.v. only), oxaliplatin, papayerine HCl, pentamidine, pimozide, probucol, procainamide, propofol, quinidine, roxithromycin, sevoflurane, sotalol, sparfloxacin, sulpiride, terfenadine, thioridazine, vandetanib |
| Herbal preparations/medications | Herbal preparations/medications known as strong inducers or inhibitors of CYP3A4/5 or those with a known risk of QT prolongation are prohibited throughout the study. These herbal medications include, but are not limited to: St. John's wort, Kava, ephedra (ma huang), gingko biloba, dehydroepiandrosterone (DHEA), yohimbe, saw palmetto, and ginseng. Patients should stop using these herbal medications 7 days prior to first dose of study drug |
| Other investigational and antineoplastic therapies | Other investigational therapies must not be used while the patient is on the study. Anticancer therapy (chemotherapy, biologic or radiation therapy, and surgery) other than the study treatments must not be given to patients while the patient is on the study medication. If such agents are required for a patient then the patient must be discontinued study drug. |

¹ NTI = narrow therapeutic index drugs whose exposure-response indicates that increases in their exposure levels by the concomitant use of potent inhibitors may lead to serious safety concerns (e.g., Torsades de Pointes).

² Herbal product

³ P-gp inducer

⁴ Source: www.qtdrugs.org (as of August 23, 2017)

As far as possible, avoid co-administration of QT prolonging drugs or any other drugs with the potential to increase the risk of drug-related QT prolongation (e.g., via a potential DDI that increases the exposure of ribociclib or the exposure of the QT prolonging drug). A definitive list of drugs with a known risk, possible risk, or conditional risk of QT prolongation and/or Torsades de Pointes (TdP) is available online at qtdrugs.org.

3 General Strategies for Data Presentation

All categorical data will be summarized by frequencies and percentages. Wherever categorical data is missing, a 'Missing' row will be included at the bottom with frequencies and percentages presented for it.

Continuous data will be summarized with either standard descriptive statistics (i.e. the number of non-missing data points, arithmetic mean, 25th and 75th percentiles, standard deviation, minimum, median and maximum), or will be grouped into categorical data and summarized as categorical data.

All collected data will be listed.

3.1 Patient disposition, demographics and other baseline characteristics

3.1.1 Patient disposition

3.1.1.1 End of treatment phase disposition

The number of patients who are enrolled and treated as well as those who discontinued the study (along with their reasons for premature discontinuation) or are still ongoing in the study at the time of the analysis will be summarized for FAS by dose cohorts of Phase I and by groups of Phase II.

A listing of study completion by dose cohorts of phase I and groups of phase II will be produced using the FAS. Patients are considered to be ongoing if they have not discontinued due to any reason.

The possible reasons for discontinuation of study treatment are as follows:

- Adverse events
- Lost to follow up
- Physician decision
- Pregnancy

- Protocol Deviation
- Technical problems
- Subject/Guardian decision
- Death
- Progressive disease
- Study terminated by the sponsor

A listing for data on final status of the patient in the study will be provided. A data listing of screened patients who did not take study drug will be also provided with reasons for screening failure.

3.1.2 Demographic and baseline characteristics variables

Demographic and baseline characteristics data will be summarized using the FAS. All demographic and background data will also be listed.

The following variables will be summarized by dose cohorts of Phase I and by groups of Phase II:

- Age [years]
 - Age categories
 - ≤ 40
 - $>40 - \leq 60$
 - $>60 - \leq 75$
 - >75
 - missing
 - Sex
 - Male
 - Female
 - missing
 - Race
 - Asian
 - Black
 - White/Caucasian
 - Native American
 - Pacific Islander
 - Unknown
 - Other
 - missing
 - Ethnicity
 - Hispanic/latino
 - East Asian
 - Chinese
 - Japanese
 - Korean
 - Other East Asian

- South East Asian
 - Thai
 - Malay
 - Vietnamese
 - Cambodian
 - Laotian
 - Indonesian
 - Filipino
 - Other South East Asian
 - South Asian
 - Indian
 - Pakistani
 - Other South Asian
 - West Asian
 - Turkish
 - Arabian
 - Persian
 - Lebanese
 - Other West Asian
 - Russian
 - Mixed Ethnicity
 - Not Reported
 - Unknown
 - Other
 - Missing
- Child bearing status for female patients
 - Able to bear children
 - Premenarche
 - Post menopausal
 - Sterile-of child bearing age
- ECOG PS
 - 0-Fully active, able to carry on all pre-disease performance without restriction
 - 1- Restricted in physically strenuous activity but ambulatory and able to carry out work of a light or sedentary nature, e.g., light house work, office work
 - 2- Ambulatory and capable of all self-care but unable to carry out any work activities. Up and about more than 50% of waking hours
 - 3- Capable of only limited self-care, confined to bed or chair more than 50% of waking hours
 - 4- Completely disabled. Cannot carry on any self-care. Totally confined to bed or chair
 - 5- Dead
 - Missing
- Body weight [kg]
- Body weight categories
 - <55

- 55-75
 - ≥ 75
- Body height [cm]
- Body Mass Index (BMI) [kg/m^2]
- BMI categories
 - <30
 - ≥ 30

All categorical data will be summarized by frequencies and percentages. Continuous data will be summarized with standard descriptive statistics.

